7.2 Inclusion Criteria

1. Female
2. Age 18-50 years
3. English-literate
4. Willingness to provide informed consent
5. Meeting criteria for diagnosis of VBD based on scoring a 3 or greater on a scale of 0-10 (with 0 being no pain and 10 being the worst pain imaginable) for either the
 - a. Tampon test
 - b. Pain with sexual contact involving penetration into the vagina
 - c. Pain with touch to the vaginal opening

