12 OUTCOME DETERMINATIONS

Aim 1. Determine the efficacy of peripheral, central, and combined treatments in alleviating pain among women with VBD-p and VBD-c.

Primary Endpoints:

- Ia. pain score during tampon test at 16 weeks
- Ib. self-reported pain *via* SF-MPQ at 16 weeks

Secondary Endpoints:

- Ila. experimental pain *via* local and remote PPTs at 16 weeks
- Ilb. COPC pain levels *via* COPC follow-up survey at 16 weeks
- Ilc. Pain scores and PPTs at 8 weeks and 24 weeks

Aim 2. Determine the efficacy of peripheral, central, and combined treatments in improving patient reported outcomes among women with VBD-p and VBD-c.

Primary Endpoints:

- Ia. self-reported physical/mental health *via* SF12v2 at 16 weeks
- Ib. sexual health *via* PROMIS at 16 weeks

Secondary Endpoints:

- Ila. mood *via* SCL-27 at 16 weeks
- Ilb. somatic awareness *via* PILL at 16 weeks
- Ilc. perceived stress *via* PSS at 16 weeks
- Ild. sleep *via* sleep scale at 16 weeks
- Ile. Patient reported outcomes at 8 weeks and 24 weeks

Aim 3. Determine the efficacy of peripheral, central, and combined treatments in normalizing cytokine and microRNA expression profiles in vaginal and blood tissues collected from women with VBD-p and VBD-c.

Primary Endpoints:

- Ia. cytokine levels *via* mesoscale discovery assays at 16 weeks
- Ib. microRNA levels *via* sequencing read at 16 weeks

Secondary Endpoints:

- Ila. cytokine and microRNA levels at 8 weeks and 24 weeks
- Ilb. Aim 3 will also identify cytokine and microRNA biomarkers at baseline that predict treatment response at 8, 16, and 24 weeks

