15.2 Analysis of the Aim 1 Endpoints

Primary endpoints will be the net change in vaginal vestibule pain following treatment measured using the Tampon Test and the Short-Form McGill Pain Questionnaire (SF-MPQ).

- The Tampon Test will provide a self-reported numeric rating scale of pain with self-tampon insertion, performed by the patient and reported to the research nurse. An Original Regular Tampax tampon will be inserted by the participant into her vagina and then she will be asked to verbally rate the pain on a scale of 0-10, with 0 meaning no pain and 10 meaning the worst possible pain. The Tampon Test has good reliability, construct validity, and responsiveness and is a recommended outcome measure for VBD clinical trials.⁹⁶
- The SF-MPQ measures perceived sensory qualities of pain using 11 descriptors and affective qualities related to pain using 5 descriptors. Responses on 4-point scales are summed to compute scores for each section.⁹⁷ SF-MPQ subscales have been successfully used to quantify treatment responses in trials for VBD and vulvodynia.⁹⁸⁻¹⁰⁰

Secondary endpoints include changes in pressure pain thresholds (PPTs) measured at the

- Vaginal Vestibule PPT will be determined using a digital vestibular algometer applied to 3 externally-accessed sites (2 and 10 o'clock on the upper vestibule and 6 o'clock on the lower vestibule) beginning at 1N and increasing until the participant's first sensation of pain or a maximum applied pressure of 10N.¹⁰²
- Levator Muscle Complex PPTs will be determined in a similar manner by applying the algometer internally to the right, midline, and left puborectalis levator muscles sites (5, 6, and 7 o'clock) just lateral to the perineum.
- Remote Bodily PPTs will be determined in a similar manner by applying the algometer to 3 'neutral' non-pelvic body sites (deltoid, shin, and trapezius), right and left, and calculating a composite score.

Data Analysis. The two primary statistical questions for Aim 1 are: 1a) Is peripheral treatment with lidocaine/estradiol compound cream, or central treatment with nortriptyline, or a combination of both treatments more effective for either VBD subtype than placebo? 1b) Is peripheral treatment more effective than central treatment in VBD-p, and is central treatment more effective than peripheral treatment in VBD-c?

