To answer questions 1a and 1b, we will fit mixed model repeated measures (MMRM) models which account for missing data as an integral part of the analyses under the assumption of ignorable missing. To answer question 1a, the MMRM model includes longitudinal pain score (0-10 NRS on Tampon Test) as a continuous outcome variable; includes fixed effect terms for treatment (nortriptyline, lidocaine/estradiol, and their interaction), visit, treatment visit interaction, center, and fixed effect covariates vector including age, VBD subtype (binary variable where VBD-c is coded as 0 and VBD-p coded as 1), race (three levels "white", "black" and "other" race, coded into two binary dummy variables with European American serving as a reference level).

Overall treatment effect of nortriptyline, lidocaine/estradiol, and their interaction will be evaluated using an F-test. If significant ($p < 0.05$), treatment differences (each of 3 treatment groups minus placebo) in the Least-Squares means (LS means), their 2-sided 95% CIs, and associated p-

values will be estimated from the MMRM model. P-values will be compared with the significance threshold Bonferroni-corrected for 3 tests (i.e. alpha 0.0166).

To answer question 1b, we will fit a MMRM model analogous to 1a, with additional terms of VBD subtype visit interaction, treatment VBD subtype interaction, and treatment visit VBD subtype interaction. The significance of the additional interaction terms will be evaluated using a F-test comparing the full model in 1b and the reduced model in 1a. Significant ($p < 0.05$) F-test will suggest that the effect of either nortriptyline or lidocaine/estradiol cream, or both, differ by VBD subtype. In this case, we will compare the LS means of the treatment differences in each treatment-VBD-subtype subgroup, after appropriate Bonferroni correction.

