If the results for question 1a or 1b are statistically significant, the following primary outcomes will be analyzed using the same modeling strategies (models in 1a and 1b above): % decrease in pain score (tampon test) from baseline to the 16-week time point and % decrease in perceived pain on the SF-MPQ from baseline to the 16-week time point. Secondary outcomes include change in mucosal, vulvovaginal muscle, and remote bodily PPTs from baseline to the 16-week time point. Secondary outcomes also include change in pain scores and PPTs from baseline to the 8-week time point and change in pain scores and PPTs from the 16-week to the 24-week time point.

If the result for question 1b is non-significant, we will use the continuous COPC score in model 1b instead of a dichotomous VBD classification to compare treatment success for VBD-p and VBD-c. In addition, we use a binary treatment outcome (achievement of 30% pain reduction) to identify the optimal cutoff of the continuous COPC score in each treatment group.

Secondary analyses of muscle pain based on PPTs will also determine: a) the proportion of women with VBD that have a pelvic muscle pain component; b) differences in the distribution of muscle pain in VBD-p and VBD-c groups; and c) presence of muscle pain to predict treatment outcome. The latter will be tested by including the muscle pain variable (continuous or dichotomous) as part of the fixed effect term in model 1a.

Expected Outcomes. **1)** For women with VBD-p, peripheral lidocaine/estradiol treatment will be more effective than placebo or nortriptyline in reducing numeric pain ratings on the tampon test, perceived pain on the SF-MPQ, and pelvic PPTs on the algometer test at week 8 and week 16. **2)** For women with VBD-c, centrally-targeted nortriptyline treatment will be more effective than placebo or lidocaine/estradiol in reducing numeric pain ratings on the tampon test, perceived pain on the SF-MPQ, and pelvic/remote bodily PPTs on the algometer test at week 16. **3)** For women with VBD-c, combined peripheral and centrally-targeted treatments will be most effective in reducing pain on primary and secondary outcome measures at week 16. **4)** The two VBD subtypes will exhibit differential responses to treatment withdrawal at week 16, such that at the week 24 visit women with VBD-c will exhibit increases in pain after treatment withdrawal compared to women with VBD-p.

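### SF-MPQ pain, a declared Aim 1 primary endpoint, is analysed only if a tampon-test question is significant, and that condition is an either-or of two tests each at full alpha

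*Combined protocol and SAP*

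**What the plan says.** Section 2 and Section 12 list two primary endpoints for Aim 1: Ia, the tampon-test score at 16 weeks, and Ib, "self-reported pain *via* SF-MPQ at 16 weeks". Section 15.2 opens in the same way, with net change in pain "measured using the Tampon Test and the Short-Form McGill Pain Questionnaire (SF-MPQ"). No hierarchy between the two is stated.

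The models are then written for one of them. For question 1a, "the MMRM model includes longitudinal pain score (0-10 NRS on Tampon Test) as a continuous outcome variable". Question 1b uses an analogous model with added subtype interactions. Each question has an overall F-test at 0.05. Within 1a, the three comparisons with placebo follow at 0.0166. Within 1b, an unspecified Bonferroni correction follows. No alpha is divided between 1a and 1b.

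SF-MPQ enters only afterwards: "If the results for question 1a or 1b are statistically significant, the following primary outcomes will be analyzed using the same modeling strategies". The list that follows has two items: the percent decrease in tampon score, and the percent "decrease in perceived pain on the SF-MPQ from baseline to the 16-week time point". No section gives an SF-MPQ model for the case where neither question is significant. The end of Section 15.4 sends unforeseen deviations to a SAP, which does not alter this condition.

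**The concern.** The condition is placed on doing the analysis, not only on claiming significance. If the tampon result is negative, an analyst who follows the text fits no model to a declared primary endpoint, and the reader cannot tell whether SF-MPQ agreed or disagreed. Producing one primary result only when another is favourable is selective by design. Section 15.3 does not do this: each Aim 2 primary outcome gets its own model without waiting for another.

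Nor does the condition work as a multiplicity procedure. It is met if either of two tests succeeds at 0.05, and SF-MPQ is then tested by the same two models with no alpha assigned to it.

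**Working it through.** **Inputs.** Section 15.6: 400 enrolled, 20% attrition, SD 2.0, within-subject correlation 0.5, power 0.80 for 0.82 points (overall test, alpha 0.05) and for 0.98 points (each arm against placebo, alpha 0.0167). Section 5.3: allocation 1:1:1:1. Section 15.2: alpha 0.05 for 1a and 0.05 for 1b. Independence of the two tests is my assumption, and bounds without it are given.

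**1. The plan's own power figure.** Completers are 400 × 0.8 / 4 = 80 per arm. If women missing at week 16 contribute through three other visits at correlation 0.5, R² = 3 × 0.25 / (1 + 2 × 0.5) = 0.375, and the effective number per arm is 80 / (1 − 0.2 × 0.375) = 86.5.
- Pairwise detectable difference: (2.394 + 0.842) × 2 × √(2/86.5) = 0.98.
- Overall 3-df F-test, all three arms differing equally from placebo: 0.82.

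Both stated figures reproduce. On 80 completers per arm, power at the stated differences would be 0.76.

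**2. Chance that SF-MPQ is not analysed.** This is P(1a not significant) × P(1b not significant).
- Design point, no subtype effect: 0.20 × 0.95 = 0.19 (bounds without independence: 0.15 to 0.20).
- 1a and 1b both at 80% power: 0.20 × 0.20 = 0.04 (bounds 0 to 0.20).
- No tampon effect: 0.95² = 0.9025 (bounds 0.90 to 0.95).
- Completers only, effect 0.82: the condition was met in about 77% of simulated trials, so about 23% had no SF-MPQ analysis.

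**3. How often the condition is met with no effect.** 1 − 0.95² = 0.0975, and at most 0.05 + 0.05 = 0.10. Simulation (320 women, two nested 3-df F-tests at week 16, 20,000 runs per scenario) gave 0.094 to 0.100.

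**4. False SF-MPQ findings** (SF-MPQ itself unaffected by treatment).
- Large real tampon effect: the condition is almost always met, so SF-MPQ's own 1a and 1b tests give 1 − 0.95² = 0.0975 for one score (simulated 0.096 to 0.101). Section 15.2 computes a sensory and an affective score. If both were tested and independent, the figure is 1 − 0.95⁴ = 0.185.
- Tampon effect 0.82 on completers: 0.073 to 0.082 (simulated).
- No effect anywhere: about 0.01 to 0.03 (simulated, endpoint correlation 0 to 0.7).

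**5. Form of the outcome.** Section 15.2 first speaks of net change ("Primary endpoints will be the net change in vaginal vestibule pain following treatment measured using the Tampon Test"), then models the score, then lists percent decreases. A percent decrease is undefined at a zero baseline. Section 7.2 admits women on any one of three pain criteria, including "Pain with sexual contact involving penetration into the vagina", which allows a low or zero tampon score. Sections 2 and 5.2 require a tampon score of 3 or more, and Section 5.2 makes 0 to 2 a screen failure. These passages conflict.

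**The case against.** Hierarchical testing is a legitimate method, 1a and 1b are presented as separate questions, and the plan promises no family-wise rate. The tampon score itself is always analysed, and nothing forbids descriptive SF-MPQ summaries. The 19% is one design point. It would be lower with a real subtype effect, which Section 4 hypothesises. It would also be lower because the joint 1b test includes subtype-by-visit, which is not a treatment term. On assumed values (four visits, 15 df, 320 women, 50/50 split), a 0.5-point subtype difference in change from baseline would make 1b significant with probability 0.34, and the 19% becomes 0.20 × 0.66 = 13%. All of this stands. None of it supplies an SF-MPQ analysis when both questions fail.

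A reader might infer more than the documents support:
- **That family error is about 10% once the condition is met.** The 9.75% is the unconditional chance, with no effect anywhere, that a tampon test is falsely significant. False SF-MPQ findings are then only 1–3%. The SF-MPQ rate exceeds 5% when the tampon effect is real.
- **That women with a zero baseline drop out of the ITT analysis.** This arises only under Section 7.2, and only for the added percent outcome. The main tampon model uses the raw score. For SF-MPQ, no section shows that zero is possible: Table 1 gives healthy controls a stabbing score of 1.00 (SEM 0.00), which suggests items scored from 1.
- **That the secondary PPT endpoints are exempt from the condition.** They follow in the same paragraph, and their status is ambiguous.

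**Conclusion.** The point holds in this form: Aim 1 has two unordered primary endpoints, and one has a planned analysis only if the other succeeds. Assuming independent tests, SF-MPQ goes unanalysed in about 19% of trials at the plan's design point, 4% if 1b also has 80% power, and 90% with no tampon effect. The condition is an either-or of two tests at 0.05 and does not control error across the Aim 1 primaries. The relevant SF-MPQ figure is about 9.75% for one score when the tampon effect is real and large. Because no family-wise target is stated, this is absence of control rather than breach of a stated figure. If 1a is read as governing only SF-MPQ model 1a, and 1b only model 1b, each chain is at 0.05 and the total is still up to 0.10.

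**What to change.** In Section 15.2, delete the condition on doing the analysis. Fit models 1a and 1b to the SF-MPQ score through 16 weeks whatever the tampon result, and always report estimates and confidence intervals. Name the SF-MPQ score to be used. This costs no alpha; the only downside is that an unfavourable SF-MPQ result is reported.

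If a confirmatory SF-MPQ claim is wanted, restrict only the claim, by a pre-specified scheme covering both endpoints and both questions, such as a fixed sequence or graphical alpha-passing, and state its power cost. Two simpler remedies do not work. Making 1a the single condition still leaves 1a and 1b each tested at 0.05. Splitting 0.025/0.025 between endpoints, with both questions tested, gives 1 − 0.975⁴ = 9.6%.

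For scale, at 86.5 per arm:
- 1a and 1b at 0.025 each (tampon questions only): detectable differences rise from 0.82 to 0.90 (overall) and from 0.98 to 1.06 (pairwise); overall power at 0.82 falls from 0.80 to 0.71.
- Four tests at 0.0125 (both endpoints, both questions): error 1 − 0.9875⁴ = 4.9%; differences 0.96 and 1.13; power 0.61.

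A fixed sequence or alpha-passing would cost less, but the order matters: putting 1a first blocks a claim when only the subtype question succeeds.

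Make the score the analysed outcome and keep percent decrease as descriptive. Sections 2 and 5.2 must be reconciled with Section 7.2 on the tampon score at entry.

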Aching Pain	MPQ	1.14 (0.10)	1.23 (0.10)	2.06 (0.17)###	<0.0001
Tender Pain	MPQ	1.10 (0.06)	1.37 (0.13)	1.61 (0.16)**	0.003
Stabbing Pain	MPQ	1.00 (0.00)	1.13 (0.10)	1.39 (0.20)*	0.038
Unprovoked Genital Pain	GYN	0%	20%	30%	
Pain with 1 st Intercourse	GYN	N/A	67.5%	58.6%	
Pain with 1 st Tampon	GYN	N/A	51.3%	27.9%	

McGill Pain Questionnaire (MPQ), Gynecological Health Survey (GYN). MPQ data are Mean (SEM). *p<0.05, **p<0.01, ***p<0.001 vs HC. ###p<0.001 vs HC and VBD-p. GYN data are % women/ group.

Thus, qualitative and quantitative assessments of pain in the vaginal vestibule and remote body regions together with self-reported measures of perceived pain traits can distinguish women with VBD-p and VBD-c, and may be used to differentiate underlying mechanisms and indicate different pain management strategies.

3) VBD-p may be more effectively managed by peripheral therapy, while VBD-c may be more effectively managed by centrally-targeted or combined therapies. Treatment options for VBD include 1) non-medical interventions such as pelvic floor physical therapy and cognitive behavioral therapy, 2) topical medications (e.g., analgesic and hormone creams) applied to the vaginal vestibule, 3) centrally-targeted medications (e.g., tricyclics) taken orally, and 4) surgery.^{6, 10, 27} Surgical procedures such as vestibulectomy are high-risk and used as a last resort. Physical and psychological therapies are low-risk with published evidence, however are almost always used in combination with peripheral and/or centrally-targeted medications that have mixed results for successful pain management. A recent Cochrane review emphasized the need for randomized controlled trials to verify the efficacy of these commonly-prescribed medications, especially amongst different VBD subtypes.¹⁰

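### The SF-MPQ primary outcome is analysed as a percentage decrease of a score whose item coding is not stated; the result depends on that coding, and under one coding it can be undefined

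*Combined protocol and SAP*

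**What the plan says.** Section 15.2 opens the Aim 1 endpoints with "Primary endpoints will be the net change in vaginal vestibule pain following treatment", measured by the tampon test and the SF-MPQ. It describes the SF-MPQ as covering "perceived sensory qualities of pain using 11 descriptors and affective qualities related to pain using 5 descriptors" and gives the scoring in one sentence: "Responses on 4-point scales are summed to compute scores for each section".

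Later in Section 15.2, if question 1a or 1b is significant, "the following primary outcomes will be analyzed using the same modeling strategies". The SF-MPQ variable listed there is the percentage "decrease in perceived pain on the SF-MPQ from baseline to the 16-week time point". Sections 2 and 12 use a third form, the SF-MPQ value at 16 weeks.

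The plan does not say:
- whether items are coded 0-3 or 1-4;
- whether the sensory section, the affective section or a total is the endpoint;
- what to do with a baseline at the lowest possible score.

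The model to be reused adjusts for center, age, subtype and race. Section 15.2 lists no baseline pain score among the covariates.

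**The concern.** A percentage decrease has a fixed meaning only if no pain scores zero and nobody starts at zero. For a sum of 4-point items, one of these two conditions can fail whichever coding is used. If the lowest response is coded 1, the sum has a floor equal to the number of items, and complete relief falls short of 100% by an amount that depends on baseline. If it is coded 0, a woman at the floor at baseline has a zero denominator.

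This is one of the two Aim 1 primary outcomes, and the 1b model compares treatment effects between subtypes. In Table 1 of Section 3.2 the subtypes start from different MPQ levels, so a baseline-dependent percentage can differ between them when the share of pain relieved does not. Net change and percentage decrease are also different quantities, and the plan uses both for one endpoint.

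**Working it through.** The plan states no SF-MPQ percentage, standard deviation or effect size, so there is no figure to reproduce. The check is what the stated rule returns.

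**Inputs.** Section 15.2: 11 sensory and 5 affective items, each on a 4-point scale, summed by section. Section 3.2, Table 1 (earlier cohort, means): affective score 11.67 in healthy controls, 12.50 in VBD-p, 14.78 in VBD-c. Single-item means in healthy controls: stabbing 1.00 (SEM 0.00), tender 1.10, aching 1.14.

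**Formula.** Percentage decrease = 100 × (B − F)/B, with B the baseline and F the follow-up score.

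**Which coding?** A control mean of 1.00 with SEM 0.00 means that every control scored exactly 1 on stabbing. That suggests 1 = none, so 1-4 coding, in the earlier cohort. Nothing says that the trial will use it.

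**Coding 1-4, k items.** The sum runs from k to 4k.
- Largest possible decrease: 100 × (4k − k)/4k = 75%, for any k.
- Complete relief: 100 × (B − k)/B, which falls as B falls.

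The number of items behind Table 1's affective row is unclear. With 5 items the control mean is 11.67/5 = 2.33 per item, which sits badly beside single-item means of 1.00 to 1.14. With 11 items it is 11.67/11 = 1.06. Both are shown, for a woman at her group mean:

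| Assumed row | VBD-c, complete relief | VBD-p, complete relief |
|---|---|---|
| 11-item sum | (14.78 − 11)/14.78 = 25.6% | (12.50 − 11)/12.50 = 12.0% |
| 5-item sum | (14.78 − 5)/14.78 = 66.2% | (12.50 − 5)/12.50 = 60.0% |

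**Same patient, two codings.** Over 11 items, a fall from 22 to 16 under 1-4 coding is 6/22 = 27.3%. The same answers coded 0-3 fall from 11 to 5, which is 6/11 = 54.5%.

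**Effect on the subtype comparison.** Suppose treatment halves the pain above the floor in both subtypes. With 1-4 coding and an 11-item sum this reads 1.89/14.78 = 12.8% in VBD-c and 0.75/12.50 = 6.0% in VBD-p. With 0-3 coding both read 50%.

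**Coding 0-3.** Complete relief is 100% for any B above 0. If B = 0 the denominator is zero at every follow-up visit, so the woman contributes nothing and the MMRM cannot recover her. Section 7.2 admits women on a rating of 3 or more for the tampon test, penetration or touch and requires no SF-MPQ score, so a zero section score is possible. Section 15.4 places all randomised participants in the analysis.

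**Points.** The VBD-c mean minus the control mean is 14.78 − 11.67 = 3.11. If the row is an 11-item sum, recoding to 0-3 gives 3.78 − 0.67 = 3.11. A difference in points does not depend on the coding and is always defined.

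**The case against.** The strongest reply is that this is a drafting gap in a gated outcome. The models that answer 1a and 1b use the raw 0-10 tampon score, the pain sample size in Section 15.6 rests on a 0-10 scale, and the SF-MPQ percentage is reached only after a significant result. The points-based endpoint is already in the plan as net change. All of that stands, and it limits the consequence. It does not make the percentage rule computable in one agreed way.

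Four stronger readings are tempting, and the documents do not support them:

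- *Complete relief reads as 21%.* The figure (14.78 − 11.67)/14.78 = 21.0% is a fall from the VBD-c mean to the control mean. That is normalisation to the control average, not complete relief.
- *The scale has no usable zero.* Section 15.2 says only that the items have 4 points. With 0-3 coding zero is meaningful and only floor baselines fail. The 1-4 coding is inferred from an earlier cohort.
- *The women lost would be mainly VBD-p.* Table 1 gives means, not counts at zero on a section. If 1 means none, the stabbing means of 1.13 and 1.39 imply at least 87% of VBD-p and 61% of VBD-c at the floor on that item. One item is not a section sum, however, and a pain rating of 3 or more at entry makes a zero sensory score less likely.
- *The treatment comparison is biased.* The same formula applies in every arm, and no bias between arms is shown. Compression and lost values are also alternatives: each belongs to one coding, and they do not occur together.

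Points do not make an interaction scale-free either. In the halving example the changes would be 1.89 and 0.75 points. What is gained is that the answer no longer turns on an unstated code.

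**Conclusion.** The point holds in limited form. Section 15.2 describes one primary endpoint both as a net change and as a percentage decrease, and the percentage depends on a coding and a score that the plan does not state.

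With 1-4 coding the ceiling is 75%, and complete relief from the Table 1 means reads about 26% in VBD-c and 12% in VBD-p if the affective row is an 11-item sum, or 66% and 60% if it is a 5-item sum. These figures are illustrations: they assume that the earlier cohort's coding carries over and treat the group mean as one woman's baseline. With 0-3 coding the percentage behaves properly except at a zero baseline, where it has no value; the frequency of such baselines, overall or by subtype, is not shown.

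The defect is confined to this outcome. The tampon-test NRS models and the sample size are unaffected. It should be corrected before analysis because the coding can alter the apparent difference between subtypes, and a better-defined variable is already in the plan.

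**What to change.** In Section 15.2, replace the SF-MPQ percentage decrease by a named score in points: sensory section, affective section or total. If more than one is kept, say which is primary. Analyse the post-baseline scores in the MMRM with baseline SF-MPQ as a covariate, and take the week-16 active-minus-placebo difference as the estimate. This agrees with the net change that the section already names. State the item coding, and use the same description in Sections 2 and 12. Any percentage should be descriptive only, with a stated rule for a floor baseline.

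This takes a few sentences of wording and no new data, since the percentage already needs a baseline value. What is lost is a percentage headline figure for this scale.
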